172 1. To investigate whether increases in 24-h EE by cold exposure lead to increased *ad libitum* food
173 intake, as measured using a vending machine paradigm.

174 2. To determine whether the effects of increased EE due to cool temperature exposure on
175 energy intake are only concomitant with the increase in EE or persist until the following day.
176 This will be explored by repeating the cool temperature exposure intervention twice: i) once
177 inside the whole-room calorimeter with an *ad libitum* diet; and, ii) once inside the whole-room
178 calorimeter during a fixed diet, followed by one day of *ad libitum* food intake on the vending
179 machines.

180 **Secondary Aims**

181 1. To determine whether 36 hrs of fasting will result in a change in energy intake on the following
182 day, and to determine whether the decrease in 24-h EE during fasting will correlate with
183 amount of food consumed the following day.

184 2. To determine if cold exposure will alter the 24-h respiratory quotient (RQ, an approximation
185 for the ratio of carbohydrate-to-fat oxidation rates), and test whether the induced RQ changes
186 independently contribute to the altered energy intake.

187 3. To determine if the 24-h EE responses to cool temperature exposure correlate with core body
188 temperature or changes in peripheral skin temperatures, and to determine if these changes
189 are related to body adiposity or associated with food intake.

190 4. To assess if behavioral testing addressing dietary restraint, stress related eating behaviors, and
191 executive function or the responses to visual analogue scales assessing hunger modify any
192 observed EE to energy intake association.

193 5. To assess whether the above behavioral testing as measured by previously validated

194 questionnaires and tasks are associated with measured food intake or hormone

195 concentrations.

196 6. To assess if concentrations of appetitive or exercise-induced hormones will correlate with the

197 observed changes in EE and energy intake.

198 7. To determine if any observed association between EE and energy intake predicts future weight

199 change at 6 months and 1 year.

200 **HYPOTHESES**

201 **Primary Hypotheses**

202 1. An increase in 24-h EE, as induced by 24 hours of exposure to 19°C, will be associated with an

203 increase in *ad libitum* food intake, which will exceed the increase in 24-h EE, on the day of the

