204 intervention and the effect will persist for at least 24 hours.

205 2. The effect of increasing EE by cool temperature exposure on *ad libitum* food intake will be

206 evident both on the day of the intervention and the following day.

207 **Secondary Hypotheses**

208 1. Thirty-six hours of fasting will induce compensatory overeating when the subject is re-

209 introduced to food, and the decrease in 24-h EE during fasting will positively predict the

210 degree of energy consumption.

211 2. The creation of an energy deficit will lead to a decrease in RQ, but the observed changes in

212 energy intake due to changes in EE will be independent of any change in RQ.

213 3. Subjects with less body adiposity will have a greater increase in 24-h EE with cool temperature

214 exposure and a greater decrease in distal skin temperatures while more obese subjects will

215 have a smaller increase in 24-h EE with cool temperature exposure and a greater decrease in

216 proximal skin temperatures indicating greater reliance on insulating mechanisms rather than
217 adaptive thermogenesis.

218 4. Measures of executive function and results of questionnaires related to eating behaviors will
219 be associated with the amount of *ad libitum* caloric intake, but the effects of EE will be
220 independent of these relationships.

221 5. Induced increases in EE will be associated with changes in hormone concentrations, including
222 cold-induced increases in adiponectin, insulin, free T4, TSH, FGF21, glucagon, ghrelin, urinary
223 free cortisol, urinary catecholamines and decreases in leptin, GLP-1, PP and PYY, and at least
224 some of these changes will be associated with the change in food intake.

225 6. The amount of energy intake increase after an increase in EE or the ratio of Δ energy
226 intake/ Δ EE will be directly associated with weight change at 6 months and 1 year.

227 **STUDY DESIGN AND METHODS**

228 **Study Design**

229 This is a inpatient natural history, observational cohort study of healthy human research
230 volunteers with research interventions designed to understand the relationship between the
231 physiologic sensing of EE and food intake behavior. This is primarily a cross-sectional study but with a
232 longitudinal component to assess the association of baseline measurements with future weight
233 change.

234 **Subjects**

235 Sixty-eight healthy participants of all body sizes representing both genders, without evidence

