593 the 24-h EE at 19°C and 24-h EE at 24°C measured on Day 6. The CorTemp™ core body temperature
594 monitoring system will be used to assess changes in body temperature during this 24-h period.
595 Subjects will again be asked to wear 9 iButtons® to measure skin temperature changes during cool
596 temperature exposure. A 24-h urine collection will again be done for nitrogen, cortisol and
597 catecholamines. Subjects will complete the VAS at 3 time points during the approximately 23.25 hours
598 inside the calorimeter.

599 **Day 15:** Upon exiting the chamber, the subjects will complete the VAS. Fasting blood will be then
600 collected for measurement of insulin, glucagon, leptin, adiponectin, ghrelin, IGF-1, active GLP-1, PP,
601 PYY, IL-6, free T3, free T4, TSH, FGF21, estradiol and progesterone, beta-hydroxybutyrate, lactate,
602 pyruvate. Subjects will again spend 24 hrs using the vending machine paradigm, as above, for the
603 assessment of *ad libitum* food intake following the increased EE resulting from the cold-induced
604 thermogenesis during Day 14.

605 **Day 16 and 17:** This will be a wash-out period for any residual effects of the overeating expected to
606 occur during *ad libitum* food intake to wane [10]. Subjects will be fed a weight maintaining diet.

607 **Day 18:** Subjects will again reside for approximately 23.25 hrs in the respiratory chamber in a cool
608 environment (19°C), this time with access to food choices similar to those provided during the
609 assessment on Day 10. A 24-h urine collection will again be done for nitrogen, cortisol and
610 catecholamines. Subjects will complete the VAS at 3 time points during the approximately 23.25 hours
611 inside the calorimeter.

612 The amount of food intake on Day 18, as well as on Day 15, will help to determine the length
613 of time in which the cold-induced increase in EE might affect food intake, i.e. whether any EE-effect
614 on energy intake only occurs during cooler temperature exposure or whether the effect persists until
615 the following day. The amount of food intake consumed inside the metabolic chamber on Day 18 at
616 19° C will be compared to that obtained on Day 10 at 24°C in the same setting to evaluate the
617 difference in energy intake during the cool temperature exposure.

618 **Days 19 and 20:** This will be a washout period for any residual effects of the overeating expected to

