645 estradiol and progesterone (women only). Urine pregnancy test (β -hcg) will be done in females only.
646 The DXA scan will not be performed if the pregnancy test is positive.

647 **Blood Withdrawal**

648 Blood withdrawal will remain within the NIH guideline of <10.5 mL/kg or <550 mL (whichever
649 is smaller) every 8 weeks for research purposes. The total amount of blood drawn is detailed below.

650

651

Tests	Amount
Screening lab work	32 mL
OGTT	151 mL
Fasting blood measurements	
EBL chamber (pre- and post-)	76 mL
CIT chamber (pre- and post-)	60 mL
FST chamber (pre- and post-)	60 mL
Total (baseline admission):	379 mL
Outpatient visits	
6 months	32 mL
1 year	32 mL
Total:	443 mL

652

653 **Sample Size Calculation**

654 The sample size calculation to answer the primary research question is based on the number
655 of patients needed to demonstrate an association between any change in EE due to interventions and
656 subsequent change in energy intake. In preliminary analyses using data from our clinical research unit
657 [13], the cross-sectional Pearson correlation between unadjusted 24-h EE during energy balance and
658 energy intake is 0.46 ($p<0.0001$). A target sample size of 46 participants will provide a power of
659 greater than 0.80 with an alpha of 0.05 to detect a 0.40 correlation ($r^2=0.16$) using simple linear
660 regression assuming that the association between change in EE and change in energy intake will be
661 the same as that between EE and energy intake. However, any finding will subsequently be adjusted
662 in multivariate linear regression analysis for age, sex, race, fat mass and fat free mass (5 covariates),
663 which requires a minimum of 50 volunteers. In addition, given the number of analyses that will be
664 done, an alpha of 0.01 is likely more appropriate. Therefore, to detect a correlation of 0.4 with a
665 power >0.80 at an alpha = 0.01, a total of 68 subjects will be enrolled for the core study (Table 2).

666

667 **Table 2. Sample size calculations achieving a statistical power ≥ 0.8 .**

	$\alpha=0.05$	$\alpha=0.01$	$\alpha=0.005$	$\alpha=0.001$
r=0.50	n=29	n=41	n=47	n=59
r=0.40	n=46	n=68*	n=77	n=98
r=0.30	n=84	n=124	n=142	n=181

668 r: Pearson's unadjusted correlation between change in EE and change in energy intake

669 α : significance level (2-sided)

670 *: Sample size for the final analysis

671

672 An interim analysis will be conducted when a target sample size of 47 subjects complete the

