673 baseline admission. This sample size will provide 80% power ($\alpha=0.005$) to detect a simple

674 correlation of 0.5 between change in EE due to any intervention and change in energy intake. The

675 alpha level for this interim analysis is set to 0.005 based on the alpha spending function approach

676 [[64, 65]]. The alpha level for the final analysis will remain at 0.01. More importantly, the interim

677 analysis will allow us to assess whether there is likely to be a significant correlation once the full

678 sample size is reached or whether the null hypothesis is highly likely to be accepted. If the correlation

679 within the first 47 subjects is <0.2 , the study will be stopped as the null hypothesis will be highly likely

680 to be accepted. However, if the correlation is much stronger than anticipated, the study will continue

681 to obtain adequate sample size for adjusting for covariates and answering the secondary research

682 questions. If the interim correlation is between 0.2 and 0.4, the final sample size will be increased

683 from 68 to 124 subjects to provide 80% power at an alpha of 0.01 to detect a more moderate

684 association. Achieved power as a function of final sample size, alpha and correlation value between

685 change in EE and energy intake is reported in Table 3. Assuming a 30% dropout rate, we will ask for a

686 total enrollment of 160 subjects.

687

688 **Table 3. Power calculations based on different values of alpha (α), correlation value (r) and**
 689 **sample size (n).**

α	r	n	Power
0.001	0.30	47	0.103
		68	0.208
		124	0.544
	0.40	47	0.308
		68	0.547
		124	0.915
	0.50	47	0.635
		68	0.873
		124	0.997
0.005	0.30	47	0.223
		68	0.378
		124	0.727
	0.40	47	0.503
		68	0.732
		124	0.969
	0.50	47	0.803*
		68	0.949
		124	0.999
0.01	0.30	47	0.301
		68	0.470
		124	0.799
	0.40	47	0.598
		68	0.804**
		124	0.982
	0.50	47	0.863
		68	0.969
		124	1.000

690 *: interim analysis

691 **: final analysis

692
 693 **Data Analysis**

694 Our primary outcome will be the association between the change in EE and the change in
 695 energy intake induced by the interventions (cool temperature exposure and fasting). As the purpose
 696 of this protocol is to evaluate the effects of altered EE on food intake regardless of the type of
 697 intervention, only within-subject analyses rather than between-interventions analyses will be carried

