698 out to evaluate the EE response to each intervention compared to energy balance. For descriptive
699 statistics, normally distributed variables will be described with means and standard deviations,
700 skewed variables will be described with medians and interquartile range. Baseline differences in
701 demographics between sexes and races will be assessed using Student's *t*-test or one-way ANOVA,
702 respectively. Determinants of the EE response to interventions will be determined using mixed
703 models to account for repeated measures and including the variables age, sex, race, percentage body
704 fat, aerobic capacity and type of intervention as fixed effects. The diagonal (DIAG), the compound-
705 symmetry (CS) and the first-order autoregressive (AR1) covariance structures will be considered for
706 estimation of the random effect of the within-subject repeated measures. The model fit of all
707 calculated models will then be compared using the Bayesian information criterion (BIC) statistic to
708 select the best model in terms of covariance structure for random effects and the number of
709 predictors (i.e., lowest BIC). Post-hoc tests comparing interventions to 24-h EE during energy balance
710 will be conducted using the Dunnett's test to correct for multiple comparisons.

711 The change in 24-h EE during each intervention will be calculated as the absolute change in
712 kcal as well as percent change compared to energy balance. Similarly, change in 24-h RQ,
713 carbohydrate and fat oxidation rates, sleeping EE and sleeping RQ will be also calculated and
714 considered in the analyses. Changes in *ad libitum* food intake due to interventions will be calculated
715 as absolute kcal change as well as percent change in weight maintaining energy needs. Associations
716 between continuous variables will be quantified by Pearson's *r* for data that are normally distributed
717 and Spearman's ρ for data not normally distributed. These analyses will include correlations among
718 changes in 24-h EE during fasting and cool temperature exposure to uncover those EE responses that
719 share common underlying mechanisms, and the association between the EE responses and

720 concomitant and subsequent *ad libitum* food intake. Multivariate regression models will be calculated
721 to control for potential confounders including age, sex, race, aerobic capacity, fat mass and fat free

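### Primary Aim 2 asks whether the cold effect on intake is same-day only or persists, but no planned analysis compares the two days or bounds the next-day effect

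*Combined protocol and SAP*

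**What the plan says.** All references are to the combined protocol and SAP.

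- **Primary Aims, Aim 2.** The aim is to learn whether the effects of the cold-induced EE increase on "energy intake are only concomitant with the increase in EE or persist until the following day". Cold exposure is done twice: once with free food in the chamber, and once on a fixed diet followed by a vending-machine day.
- **Primary Hypotheses, Hypothesis 2.** The effect is expected to be "evident both on the day of the intervention and the following day".
- **Intervention Phase, Day 18.** Intake on Days 18 and 15 is meant to show whether any EE effect "on energy intake only occurs during cooler temperature exposure or whether the effect persists until" the next day. The only comparator named there is for the same-day change: intake at "19° C will be compared to that obtained on Day 10 at 24°C in the same setting to evaluate the" difference during cold.
- **Data Analysis.** The plan lists the association of the EE responses with "concomitant and subsequent *ad libitum* food intake. Multivariate regression models will be calculated" to adjust for confounders.
- **Sample Size Calculation.** To detect one correlation of 0.4 with "power >0.80 at an alpha = 0.01, a total of 68 subjects will be enrolled". Table 3 gives that power as 0.804. After an interim look at 47 completers, the study stops if the correlation is below 0.2 and grows to 124 if it lies between 0.2 and 0.4.

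**The concern.** Aim 2 is a choice between two states. Choosing *same-day only* needs evidence about the next-day effect itself: that it differs from the same-day effect, and that it is too small to matter. Two separate tests supply neither. If one gives p<0.01 and the other does not, the difference between them may be chance, and a non-significant next-day result does not show absence.

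The other planned analyses do not fill the gap:

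- The mixed model that includes type of intervention has the EE response as its outcome, not intake.
- The Day 18 versus Day 10 comparison gives the same-day change only.
- The sequence variable and its t-tests compare the two randomised orders, not the two intake days.

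At stake is one of the two primary aims. A finding that the effect stops with the cold could be reported when the two effects are equal. A contrast added after a split result has been seen would be post hoc.

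**Working it through.** **Inputs from the document:** r=0.40 (design value) and r=0.30 (the enlarged-sample case); n=68, 124 and interim 47; two-sided alpha 0.01.

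**Assumed:** the correlation between the residuals of the two intake changes, which the document does not give. The range used is 0 to 0.5, with 0.9 as an extreme. The vending-machine reproducibility of 0.9 quoted in the protocol concerns intake levels, not changes.

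**Step 1: the plan's own figure.** Fisher z power = Φ(atanh(r)·√(n−3) − 2.576). For r=0.40 and n=68, 0.4236 × √65 = 3.416; 3.416 − 2.576 = 0.840; Φ(0.840) = 0.7995. With the small-sample bias term it is 0.806. The stated 0.804 is reproduced, as power for one correlation.

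**Step 2: two tests, independence approximation.** With p=0.804 for each test:
- both significant: p² = 0.646
- same-day only: p(1−p) = 0.158
- exactly one: 2p(1−p) = 0.315

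**Step 3: simulation with equal true effects.** 20,000 trials per setting, one EE response per person, two intake changes, and each correlation tested at 0.01. Ranges run over residual correlation 0 to 0.5.

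| True r, n | Same-day only | Exactly one | Both |
|---|---|---|---|
| 0.40, 68 | 11-15% | 22-30% | 0.65-0.69 |
| 0.30, 68 | 16-24% | 33-48% | 0.23-0.30 |
| 0.30, 124 | 11-15% | 23-31% | 0.65-0.68 |

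At residual correlation 0.9, r=0.40 and n=68, same-day only falls to about 5%. A direct test of the slope difference rejects in about 1% throughout, which is simply its alpha.

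**Step 4: with the interim rule.** The plan does not say which correlation drives the interim decision, so both the same-day value and the larger of the two were tried. At r=0.40 the sample is enlarged to 124 in about 25-42% of trials. Same-day only then occurs in 6-10%, and both are significant in 0.78-0.86. At r=0.30 the figures are 13-21% and 0.47-0.56.

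**Step 5: what a contrast can deliver.** With true r=0.40 same-day and 0 next-day, the slope-difference test at alpha 0.01 has power of about 0.41-0.76 at n=68. With 0.40 and 0.20, where the effect is weaker but does persist, it is significant in 8-19% of trials at n=68 and 17-39% at n=124. A significant difference therefore cannot by itself mean that the next-day effect is absent.

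**Step 6: what the next-day interval can deliver.** At n=68 the 99% half-width on the z scale is 2.576/√65 = 0.320. If the relevant effect were set at r=0.40, for illustration, the interval excludes it when the observed next-day r is below tanh(0.4236 − 0.320) ≈ 0.10.

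**The case against.** Several points on the other side stand.

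- **A reader might infer that the plan forbids this comparison**, because it says that for each type of "intervention, only within-subject analyses rather than between-interventions analyses will be carried" out. The document does not support that reading. The sentence goes on to the EE response relative to energy balance, and the interventions are defined as cold and fasting. Same-day against next-day is a within-subject comparison inside one intervention, and nothing rules it out.
- **A reader might infer that the investigators will read a split in significance as same-day only.** The plan states no reading rule, so this is a possibility that it leaves open. With equal true effects, about half of such splits at fixed n would go the other way.
- **A reader might infer that the stated power is wrong.** It is not. It is given for an association, it reproduces, and no joint power is claimed. Hypothesis 2 can be tested by requiring both associations.
- **Fixed n=68 overstates the problem at r=0.40**, because the interim rule sometimes raises the sample to 124. Hence both sets of figures above.
- **The study calls itself proof-of-concept**, and the text for Day 18 says only that the two days will help to determine duration.

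None of this supplies an analysis that can support the same-day-only answer.

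**Conclusion.** The gap is real but limited. The plan can test each day and can test Hypothesis 2, but it has no analysis that compares the two effects or bounds the next-day one, so the same-day-only arm of Aim 2 could rest on a split in significance.

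Under equal effects of r=0.40, the misleading pattern has a chance of about 11-15% at fixed n=68 and about 6-10% under the interim rule. It is more common at r=0.30. These figures rest on an assumed residual correlation of 0 to 0.5, fall if the true value is higher, and cover the correlation analyses only. Joint power for Hypothesis 2 at r=0.40 is about 0.65-0.69 with N fixed at 68, and higher if N is enlarged. This is an inexpensive improvement to a primary aim; it does not show that the design or the sample size calculation is in error.

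**What to change.** Before results are seen, add to Data Analysis:

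1. **One within-subject mixed model for intake.** Stack the same-day change (Day 18 minus Day 10) and the next-day change (Day 15 minus its baseline from the vending days that follow the 24°C chamber session). Each change uses its own comparator because the settings differ. Include EE response, day, and EE response × day. Name the EE response and the vending baseline used.
2. **Two reported quantities, each with a 99% CI:** the EE response × day term and, separately, the next-day slope.
3. **A reading rule.** Do not conclude same-day only from a non-significant next-day result, nor from a smaller next-day slope alone. Require the next-day CI to exclude a relevant effect stated in advance; otherwise report the question as unresolved.
4. **A sentence on power.** Say that 0.80 applies to one association, and that joint power for Hypothesis 2 is about 0.65-0.69 at r=0.40 with N=68, under the stated assumption on residual correlation.

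The cost is SAP wording and one extra model on data already being collected. Some results will be called unresolved, because the contrast has power of only about 0.41-0.76 at n=68 even if the next-day effect is zero.

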: 24 hours inside the metabolic chamber (*ad libitum* diet)

Quest.: self-administered questionnaires and computerized tasks

OGTT: oral glucose tolerance test

DXA: dual energy X-ray absorptiometry for body composition assessment

VO₂ max: graded-cycle ergometry

Chamber: 24-h measure of EE in the metabolic chamber

Vending: computerized vending machines for *ad libitum* food intake measurement

332 Volunteers will provide informed consent prior to entering the study. Subsequently, they will
333 be screened and interviewed for eligibility. During screening, a medical history will be obtained as
334 well as a physical exam and resting 12 lead electrocardiogram. Blood will be drawn for screening tests
335 including complete blood cell count, platelet count, glucose, electrolytes, urea nitrogen, creatinine,
336 liver function tests (total protein, albumin, bilirubin, AST, ALT, gamma-GT, alkaline phosphatase),
337 thyroxine stimulating hormone (TSH), calcium and phosphorus. Urine will be collected for complete
338 urinalysis, urinary hCG (pregnancy test for females only) and drug testing. All subjects who meet
339 inclusion and exclusion criteria and agree to participate will be admitted to the clinical research unit
340 for about 23 days to complete the study. Initial demographic information will be collected on all
341 subjects including comorbidities, race, gender, weight, height and waist, thigh and neck
342 circumferences. There is nursing staff available 24 hours a day.

343 **Randomization**

344 Randomization will be done using a permuted block randomization design with a block size of
345 6 stratified by sex to account for potential order effects of cold interventions (described below).
346 Specifically, half the subjects will undergo first the assessment of *ad libitum* food intake on the
347 vending machines the day following the cold intervention inside the metabolic chamber (as shown in
348 Figure 1,), with the other half undergoing first the *ad libitum* food intake assessment the day of the
349 cold exposure inside the metabolic chamber (Figure 1). The random allocation sequence will be
350 created by a statistician who does not have subject contact.

351 **Admission**

352 A description of the inpatient phase of the study is provided below. The specific day numbers on which
353 procedures occur represent a common scenario. The precise day may vary due to normal subject scheduling

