722 mass. In evaluating the relationship between altered EE by cool exposure/fasting and *ad libitum* food
723 intake, the concomitant RQ will also be included as further covariate in the multivariate model. Lastly,
724 sensitivity analyses accounting for the SPA inside the metabolic chamber will be done. Although we
725 anticipate that the wash-out period will remove any carry-over effect, potential order effects arising
726 from the cross-over design of the study will be assessed by including a dichotomous variable for the
727 sequence effect of interventions (e.g., 0 = “cold exposure & subsequent *ad libitum* food intake”; 1 =
728 cold & concomitant *ad libitum* food intake) in the multivariate models assessing the association
729 between change in EE and change in energy intake. Student t-tests will be also calculated to
730 determine if the change in EE or the change in energy intake differ between these two groups. If no
731 difference exists in the outcome variables between these 2 groups and the dichotomous variable is
732 not significant in the multivariate model, we will determine that no evidence for an order effect exists
733 and leave the dichotomous variable out of the final multivariate model. If there will be evidence of an
734 order effect, we will include the dichotomous variable in the multivariate model to ‘adjust’ for the
735 order effect.

736 To follow-up the regression analyses and assess potential causality linking EE to energy intake,
737 mediation analysis based on hierarchical multiple regression models as outlined in [66] will be used to
738 evaluate whether the effect of increased EE on energy intake is exerted through the influence of
739 mediators, including hormonal changes, RQ appetite sensations, behavioral and neurocognitive
740 scores. The Sobel test [67] will be used to test the significance of the mediation effect.

741 For all hormonal measures, the change in concentrations induced by the interventions will be
742 compared to the baseline fasting concentrations drawn prior to the energy balanced 24-h EE
743 assessment using paired t-tests for normally distributed data or the Wilcoxon nonparametric test for
744 skewed data. A sample size of 68 subjects will provide greater than 80% power with an alpha of 0.05
745 to detect a minimum mean expected decrease in fasting leptin, as a representative hormone, of
746 -1.8 ± 6.0 ng/mL as observed in prior studies measuring leptin concentrations during 24-h fasting [1].

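### For energy expenditure as an outcome, the randomised order of the two cold sessions is checked only by an unpaired t-test, and the EE-response model has no first-versus-second-session term

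*Combined protocol and SAP*

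**What the plan says.** Randomization allocates participants 1:1, in permuted blocks of 6, to the order of the two cold sessions, "stratified by sex to account for potential order effects of cold interventions". Under Intervention Phase each participant has both sessions: one on a fixed diet followed by a day on the vending machines (Days 14-15), and one with ad libitum food inside the chamber (Day 18).

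Data Analysis checks order in two ways:

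- A 0/1 sequence variable enters the multivariate models that relate change in EE to change in intake. EE is a predictor there, not the outcome.
- Student t-tests are used to "determine if the change in EE or the change in energy intake differ between these two groups".

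If both are null, the plan is to declare no evidence of an order effect "and leave the dichotomous variable out of the final multivariate model". Otherwise the variable stays in that EE-intake model.

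The mixed model for the EE response is specified separately. It lists age, sex, race, percentage body "fat, aerobic capacity and type of intervention as fixed effects". It has no order, period or sequence term, and a positive t-test does not add one. The plan does not say which change in EE the t-test uses (one session, each session, or a combination), nor at what alpha.

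**The concern.** A difference between the first and second cold exposure, for instance through habituation, is a period effect. In a two-period crossover it appears within each person, with opposite sign in the two sequences. A between-group test on one session sets that effect against the full between-person variance. A test on the average of the two sessions cannot see it at all.

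The change in EE is the exposure in the primary association, and order was randomised so that such an effect could be handled. What is at stake is whether a finding of no order effect on EE is well supported, and whether period variation is left in the residual of the EE model.

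**Working it through.** **Inputs.** From the documents: N = 68 (Sample Size Calculation), hence 34 per sequence; N = 124 if the interim rule enlarges the study; alpha 0.01 for primary and 0.05 for secondary analyses, with none stated for the order test. Not in the documents: the SD of the change in EE (written SD, taken as equal in the two sessions), the correlation rho between the two cold changes, and the size of any order effect. Results are therefore in SD units over a range of rho.

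**The plan's own figure.** There is none for the order test. The figure that fixes N reproduces: for r = 0.40, n = 68, alpha 0.01, Fisher's z gives 0.4236 × √65 = 3.416; 3.416 − 2.576 = 0.840; power 0.80. Table 3 states 0.804.

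**Step 1: what each test sees.** Let A be the fixed-diet and B the ad libitum cold session, with mean changes a and b, and let δ be the effect of being second.

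| | Sequence A then B | Sequence B then A | Difference between sequences |
|---|---|---|---|
| Session A alone | a | a + δ | δ |
| Session B alone | b + δ | b | −δ |
| Mean of A and B | (a + b + δ)/2 | (a + b + δ)/2 | 0 |
| A − B within person | a − b − δ | a − b + δ | 2δ |

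A test on the mean of the two sessions rejects at its alpha whatever δ is. For the same reason, a person-level sequence term in a model stacking both sessions would not capture δ.

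**Step 2: standard errors.**

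- Unpaired, one session: SD × √(2/34) = 0.243 SD.
- Within person: the variance of A − B is 2 SD²(1 − rho), and δ is half the difference between sequences, so SE = SD × √((1 − rho)/34). This is 0.171 SD at rho = 0 and 0.121 SD at rho = 0.5.

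The within-person SE is smaller by a factor of 1.4 at rho = 0 and 2 at rho = 0.5.

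**Step 3: effect detectable with 80% power (noncentral t).**

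| | Unpaired, one session | Within person, rho = 0 | Within person, rho = 0.5 |
|---|---|---|---|
| N = 68, alpha 0.05 | 0.69 SD | 0.49 SD | 0.35 SD |
| N = 68, alpha 0.01 | 0.85 SD | 0.60 SD | 0.425 SD |
| N = 124, alpha 0.05 | 0.51 SD | 0.36 SD | 0.25 SD |

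At N = 68 the unpaired test has under 50% power for effects below about 0.48 SD (alpha 0.05) or 0.64 SD (alpha 0.01).

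**Step 4: if each session is tested.** Power at N = 68, alpha 0.05, rho = 0.5 (the either-session column simulated, 20,000 runs):

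| δ | One session | Either session positive | Within person |
|---|---|---|---|
| 0 | 0.05 | 0.09 | 0.05 |
| 0.2 SD | 0.13 | 0.25 | 0.37 |
| 0.3 SD | 0.23 | 0.45 | 0.68 |
| 0.4 SD | 0.37 | 0.67 | 0.90 |
| 0.5 SD | 0.53 | 0.85 | 0.98 |

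Two t-tests narrow the gap, but at a false-positive rate of about 9%.

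**Step 5: consequence for the EE model.** If δ is not modelled, the A − B difference varies by ±δ with sequence, which adds δ² to its variance. At rho = 0.5 that variance is SD², so δ = 0.3 SD adds 9% and δ = 0.5 SD adds 25%. With 34 v 34 the contrast between the two cold sessions is unbiased. At an illustrative 37 v 31 the bias is (37 − 31)/68 = 9% of δ.

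**The case against.** The strongest reply has four parts.

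- **The planned checks act together.** Change in EE is calculated for each intervention, and an order effect is ruled out only if the outcomes do not differ and the sequence term is non-significant. One positive result is enough to keep the variable. This stands, and it is why it cannot be said that a real order effect would usually be missed: Step 4 gives 0.85 for either session at 0.5 SD. But any such result changes only the EE-intake model, and the false-positive rate rises.
- **The primary association already carries order.** When one cold session per person is analysed, sequence is the same as first-versus-second exposure for that session, and sex is a covariate in those models. This stands.
- **A large order effect is not indicated.** The Introduction cites a study in which 24-h cold-induced thermogenesis was the same after a month at 24°C and a month of overnight 19°C. That argues against strong habituation. It does not remove the reason the plan gives for randomising order.
- **A between-sequence comparison is a recognised check for carry-over.** This is true, and a period term does not isolate carry-over. The t-test is still the weaker tool for a first-versus-second difference, and the plan does not define the quantity tested.

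A reader might infer that the order check has little or no power, or that the EE results are biased. The documents support neither. The first needs an averaged EE change that the plan does not specify, or SDs that it does not give. The second needs sequences well out of balance.

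**Conclusion.** The point holds as one of efficiency and completeness. For EE as an outcome, the plan relies on an unpaired comparison where the design offers a within-person one, and its EE model omits the randomised factor. The smallest effect detectable with 80% power at N = 68 and alpha 0.05 could fall from 0.69 SD to between 0.35 and 0.49 SD for correlations of 0.5 to 0. This assumes equal SDs in the two sessions and a common order effect. How it translates into kcal is unknown: 50 kcal is 0.5 SD if the SD is 100 kcal but 0.25 SD if it is 200 kcal, and neither SD is in the documents. The practical harm is a less sensitive order check and some added residual variance, with negligible bias under balanced sequences. The test of the primary association does not depend on it.

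**What to change.** In Data Analysis, add a fixed effect for first versus second cold session to the mixed model for the EE response, alongside intervention type and sex, with the two cold sessions as distinct levels of type. Code it only for the cold sessions, since fasting always comes last. Retain it whatever its p-value, and exempt it from the BIC-based choice of predictors. Report its within-person estimate and confidence interval as the order check for EE, in place of the unpaired t-test.

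The cost is a wording change and one degree of freedom, on data already collected. The estimate assumes a similar order effect in the fixed-diet and ad libitum sessions, which should be stated. Do not carry the same common term over to intake: one cold session measures eating in the chamber during exposure, the other eating on the floor the next day.
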